8.1.3. Supplementary Analyses of the Primary Endpoint

The Primary Analysis described in section 8.1.1 and the Sensitivity Analyses described in section 8.1.2 will be repeated on the PPS as supplementary analyses.

8.1.4. Other Analyses of the Primary Endpoint

Summary statistics for the average number of coughs per hour in 24 hours at each visit will be presented by treatment group using the geometric mean and its 95% confidence interval for the FAS.

Subgroup analyses will be performed to evaluate the primary efficacy endpoint among subgroups of patients for the FAS. For these subgroup analyses, the primary analysis method mentioned in the section 8.1.1 will be repeated. Within this framework, the subgroups below will be analyzed:

- 1. Region (1-1: Japan, Europe, United States, 1-2: Japan, Europe and United States)
- 2. Hourly cough count at baseline (≥30 coughs/hour, <30 coughs/hour)
- 3. Cough count at Visit 1 (≥30 coughs/hour, <30 coughs/hour)
- 4. Pulmonary/Cough History (Asthma, Cough variant asthma [CVA], Gastroesophageal reflux disease [GERD], Upper airway cough syndrome including postnasal drip, rhinosinusitis, and rhinitis [UACS], Eosinophilic bronchitis including atopic cough [EB], Sinobronchial syndrome [SBS], Unexplained cough, Other, and Refractory cough, i.e., other than Unexplained cough and Other). A patient may have more than one pulmonary history. Such patients will be included in each category by pulmonary history.

A forest plot will also be provided based on the estimates for the difference of the effects of treatment at Visit 6 and its 95% Confidence Interval for the subgroups above.

The primary analysis framework will be used to assess characteristics of the dose-response relationship on the primary efficacy endpoint. The framework will be applied as originally described as well as to the log-transformed ratio of average coughs per hour in 24 hours following 4 weeks of treatment to that at baseline. The below comparisons will be presented for each of these models.

- Placebo versus 50 mg, 150 mg, and 300 mg S-600918
- Placebo and 50 mg S-600918 versus 150 mg and 300 mg S-600918
- Placebo, 50 mg, and 150 mg S-600918 versus 300 mg S-600918
- Linear Trend Test across all Treatment Groups

This framework above will be applied to the log-transformed ratio of average coughs per hour in 24 hours following 3 weeks of treatment to that at baseline, as well.

Furthermore, a three-parameter Emax model will be fitted for the ratio of the average cough count per hour in 24 hours at Visit 6 to that at baseline minus 1 to estimate the minimum, maximum, and median effect of dose on response. In this Emax model, dose will be handled in the original scale. As well, a similar Emax model will be fitted for the ratio of the average cough count per hour in 24 hours at Visit 5 to that at baseline minus 1. Responses will be plotted on a scatterplot and the fitted curve will be presented on the plot. If this Emax model fails in convergence, other models, including a linear model may be fitted.

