3.2 Rationale for Study Design and Control Group

A randomized, double-blind design was selected to minimize possible bias. Randomization will be stratified by region and the cough count at Visit 1. These stratification factors were selected in light of potential differences between Japan, Europe, and the United States in which this study is to be conducted and in light of the results of the S-600918 proof-of-concept study (Study VA322), which showed an association between cough count at screening and patient response to study drug.

Currently no drugs are approved for the treatment of patients with refractory chronic cough. Thus, placebo was selected as the control.

Evidence of the effect of S-600918 was observed 2 weeks after initiation of administration in the proof-of-concept study (Study VA322).

Thus, 4 weeks was selected as the duration of

study treatment.

[≠] At least 17 days after Visit 1

[∞] At Visit 3 (1 day after Visit 2)

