9.10.3.1 Analysis of Primary Endpoint

A mixed effect model will be applied to the common logarithm of the ratio of the number of coughs per hour in 24 hours at Visit 4, Visit 5, and Visit 6 to that at baseline as response. This model will contain treatment group, week, and the interaction between treatment group and week as fixed effect; patient as random effect; and region and the common logarithm of the frequency of coughs per hour in 24 hours at baseline as covariates. The covariance structure will be determined to be unstructured. When the mixed model with unstructured covariance fails in convergence, compound symmetry will be applied as covariance structure. Under this model, the ratio of the number of coughs per hour in 24 hours after 4 weeks of administration to that at baseline will be compared between each dose level of S-600918 and placebo. The dose-response relationship will be evaluated by a comparison of each dose level of S-600918 to placebo. This analysis will be performed for the FAS and the PPS.

Summary statistics for the number of coughs at each visit will include the geometric mean and its 95% confidence interval.

A subgroup analysis based on the combination of region and cough count at baseline will be performed and will include the following subgroups: region (Japan, Europe, and the United States) and cough count at baseline (\geq 30 coughs/hour and <30 coughs/hour). Another subgroup analysis based on the combination of region and cough count at screening (Visit 1) will be performed and will include the following subgroups: region (Japan, Europe, and the United States) and cough count at screening (\geq 30 coughs/hour or <30 coughs/hour).

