8.1.1. Primary Analysis

The null hypotheses of equality between the treatment and placebo effects will be tested using a mixed model, containing treatment group, week (as a classification term), and the interaction between treatment group and week as fixed effects; patient as random effect; and region and the common logarithm of the frequency of coughs per hour at baseline as covariates. In this model, the covariance structure will be given as unstructured, and the degrees of freedom will be derived using the Kenward-Roger method. Should the model fail to converge using the unstructured covariance, compound symmetry will be used. Using this model, the log-transformed ratio of the number of coughs per hour in 24 hours after 4 weeks of administration of study drug will be used to evaluate the null hypothesis at each dose level of S-600918 at the 2-sided alpha level of 0.05 among the FAS.

The primary analysis will summarize each of these three 2-way comparisons, presenting the estimate for the difference of the effects of treatment at Visit 6, the 95% confidence interval for this difference, and the p-value based on the hypothesis and model described above. Furthermore, the time course of the treatment effect for each treatment group will be plotted with the mean and 95% confidence interval.

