8.2. Analysis of Secondary Efficacy Endpoints

The model for the primary analysis described in section 8.1.1 provides the framework for the analysis of many of the secondary efficacy endpoints. In such cases, the only difference will be response being modelled, unless otherwise noted. For the sake of brevity, this framework will be referenced as the primary analysis framework. Wherever this framework is referenced, the corresponding 95% confidence intervals and p-values will be presented.

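### The subgroup plan pre-specifies no treatment-by-subgroup contrast, although cough count was made a stratification factor because of its link to response

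*SAP*

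**What the plan says.** SAP 8.1.4 lists four subgroup factors for the primary endpoint in the FAS: region, baseline cough count, Visit 1 cough count, and pulmonary or cough history. A patient may fall into several history categories. The method is given in one sentence: "For these subgroup analyses, the primary analysis method mentioned in the section 8.1.1 will be repeated". The display is described next: "A forest plot will also be provided based on the estimates for the difference of the effects of treatment at Visit 6", with 95% CIs.

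The model in SAP 8.1.1 has one interaction, "the interaction between treatment group and week as fixed effects". Region and log10 baseline count enter only as covariates. For each dose against placebo it reports the Visit 6 difference, "the 95% confidence interval for this difference, and the p-value based on the hypothesis and model described above".

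Protocol 9.10.3.1 is no more specific: "A subgroup analysis based on the combination of region and cough count at baseline will be performed", and the same again with the Visit 1 count. It mentions no interaction.

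Protocol 3.2 explains why cough count is a stratification factor. It cites the proof-of-concept study, "which showed an association between cough count at screening and patient response to study drug".

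**The concern.** Cough count is not a routine subgroup here. The sponsor had a reason to think that response might depend on it and built that into the randomization. The direct way to address the question is to estimate how far the treatment effect differs between the two cough-count groups, with an interval. The plan instead gives two separate sets of results.

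Two separate p-values do not test whether two effects differ. Each half of the trial has roughly even odds of reaching significance under the planned effect, so a split result is common when nothing differs. In a dose-selection study, a reader who takes such a split at face value could draw a wrong inference about which patients benefit, and do so separately for each of three doses.

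**Working it through.** **Inputs** (SAP 4.1 and protocol 9.2): difference 0.163 and SD 0.371 on the log10 ratio; two-sided 5%; 83 evaluable and 93 randomized per arm. SAP 4 makes no multiplicity adjustment. The share of patients at ≥30 coughs/hour is not given, so 50:50, 60:40 and 70:30 are assumed.

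**The plan's own figure.** The normal approximation is n = 2(1.960 + 0.842)² × (0.371/0.163)² = 81.3, so 82. The noncentral-t version gives 83, with 80.3% power. Then 83/0.9 = 92.2, so 93 per arm and 4 × 93 = 372. The stated sample size is reproduced.

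**Power within a subgroup, with the same true effect in both.** Power ≈ Φ[(0.163/0.371)√(n/2) − 1.96]. At n = 41.5 per arm this is Φ(2.001 − 1.960) = 0.517.

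**Chance that exactly one of the two is significant.** The subgroups are disjoint, so this is p₁(1 − p₂) + p₂(1 − p₁).

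| Evaluable per arm | Split | Power in each | Exactly one significant, per dose |
|---|---|---|---|
| 83 | 50:50 | 52%, 52% | 50% |
| 83 | 60:40 | 59%, 43% | 51% |
| 83 | 70:30 | 66%, 34% | 55% |
| 93 | 50:50 | 56%, 56% | 49% |
| 93 | 60:40 | 64%, 47% | 51% |
| 93 | 70:30 | 71%, 38% | 55% |

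A t-test calculation agrees at an even split: 41 per arm gives 50.3% power and 50.0% discordance, and 46 per arm gives 55.1% and 49.5%. In a simulation of 400,000 trials with a shared placebo arm and 83 per arm, at least one of the three doses shows a split result in 83% to 86% of trials.

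**Region.** With three equal regions (27.7 per arm) power is 37% in each. Significance is then not uniform across them in 1 − 0.372³ − 0.628³ = 70% of trials per dose.

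**What an interaction contrast would deliver** (83 per arm, 50:50):
- SE = 0.371 × √(2/41.5 + 2/41.5) = 0.115.
- 95% half-width = 1.96 × 0.115 = 0.226, and 10^0.226 = 1.68 on the ratio of ratios.
- Under a common effect, a 5%-level contrast is falsely significant in 5% of trials per dose, and in about 12.5% for any of three doses.
- Power is 29% if the two effects differ by 0.163 (25% at 70:30), and 81% if they differ by 0.326.
- Pooling the three doses against placebo raises the 29% to 41%.

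**The case against.** A reader might infer several stronger things that the documents do not support.

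- **That the trial cannot say whether response depends on cough count.** The ≥30 and <30 groups are disjoint, and the forest plot gives an estimate and 95% CI for each. A reader can subtract the estimates, recover each SE from its interval, and combine them as √(SE₁² + SE₂²). What is missing is a pre-specified contrast. This route is not open for the overlapping history categories.
- **That the refits are the only planned look.** SAP 8.2.2 and 8.2.4 also tabulate cough-count and LCQ responders by region and baseline cough count. These tables are descriptive and contain no interaction estimate.
- **That the plan itself produces false contrasts.** Neither document compares significance across subgroups or ties dose choice to a subgroup result. The named display is estimates with intervals. The 50% applies only if someone compares the p-values.
- **That SAP 8.2 mandates subgroup p-values.** Its sentence, "Wherever this framework is referenced, the corresponding 95% confidence intervals and p-values will be presented", introduces the secondary endpoints. Subgroup p-values follow only from repeating 8.1.1, which is a fair inference but not an explicit statement.
- **That separate unstructured covariance matrices are a serious weakness.** Three visits need six parameters, estimated over four arms (4 × 41.5 = 166 patients in an even half). That is not a difficulty for cough count. For small history categories, 8.1.1 provides a compound-symmetry fallback if the model does not converge.

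It is also fair to say that the repair has limited power. All of this narrows the point. It leaves standing that a question the sponsor randomized around has no planned estimate that answers it directly.

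**Conclusion.** The point holds as an inexpensive improvement to the analysis. The primary comparisons and their error rates are unaffected. Neither document pre-specifies a treatment-by-subgroup contrast for the primary endpoint. If the subgroup p-values are compared under a common effect, the result is split in 49-55% of trials per dose, against 5% for a formal contrast.

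The figures assume the planning effect and SD, equal splits across arms, a two-group comparison at Visit 6, and no gain from covariates or repeated visits. Better precision would lower the even-split figure: at 80% power in each half it would be 2 × 0.8 × 0.2 = 32%. The cough-count split is assumed throughout, but the result changes little over the range shown.

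The contrast would not settle whether response depends on cough count. It would show how uncertain the answer is, which two separate p-values conceal.

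**What to change.** In SAP 8.1.4:

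1. For the disjoint subgroups (Visit 1 cough count, baseline cough count, region), add a model on the whole FAS with treatment by week by subgroup and all lower-order terms. Report the Visit 6 interaction contrast for each dose against placebo with its 95% CI, as an estimate and not as a pass/fail test.
2. For cough count, also report the treatment interaction with continuous log10 baseline count.
3. For the overlapping history categories, compare patients who have the condition with those who do not, one category at a time.
4. Omit subgroup p-values or label them descriptive.

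The cost is SAP wording and a few extra model runs. No new data are needed and the primary analysis does not change. The downside is wide intervals, as shown above, and the SAP should say so in advance so that an inconclusive contrast is not read as evidence that the effect is uniform.

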8.2. Analysis of Secondary Efficacy Endpoints

The model for the primary analysis described in section 8.1.1 provides the framework for the analysis of many of the secondary efficacy endpoints. In such cases, the only difference will be response being modelled, unless otherwise noted. For the sake of brevity, this framework will be referenced as the primary analysis framework. Wherever this framework is referenced, the corresponding 95% confidence intervals and p-values will be presented.

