8.2.3. Analysis of Cough Severity (VAS)

The change in weekly cough severity at Visit 4, Visit 5, and Visit 6 to that at baseline will be analyzed using the primary analysis framework for the FAS. Similarly, the change in daily cough severity from Day 1 through Day 7 will be analyzed using the primary analysis framework for the FAS, only using Day 7 in place of Visit 6.

Both weekly and daily cough severity will also be summarized using descriptive statistics at each planned assessment by treatment group for the FAS.

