8.2.4. Analysis of Leicester Cough Questionnaire (LCQ) Score

The change from baseline at Visit 4, Visit 5, and Visit 6 of the LCQ score of each domain (Physical, Psychological, and Social) and the LCQ total score will be analyzed using the primary analysis framework for the FAS. The proportion of patients who achieved an improvement from baseline in the LCQ Total Score of \geq 1.3 at Visit 6 will be summarized descriptively for each treatment group and compared between each dose level of S-600918 and placebo using a CMH test with strata by region (Japan, Europe, United States) and cough count at baseline (\geq 30 coughs/hour, <30 coughs/hour) for the FAS. The odds ratio and its 95% confidence interval will be presented, as well. In addition, the proportion of patients who achieved this improvement from baseline in the LCQ Total Score will be summarized descriptively for each treatment group by region and cough count at baseline (\geq 30 coughs/hour, <30 coughs/hour, <30 coughs/hour, <30 coughs/hour) for the FAS.

As well, LCQ domain scores and total score will be summarized by treatment at each visit using descriptive statistics for the FAS.

During the course of the study, while still fully blinded, it was discovered that a translation error occurred in the Ukrainian translation of the LCQ. This error only affected the response options for question 16 and question 17, both of which are used in the calculation of the Psychological domain score and the Total score. As a result, the handling of the Psychological domain score and LCQ total score data for Ukrainian patients will be different, as described below.

(1) All data will be listed. (2) The analyses of Psychological domain score and LCQ Total score data described in this section will be performed excluding these patients. (3) Additional analyses of the Psychological domain score and LCQ Total score will be added where the responses for these Ukrainian patients to question 16 and question 17 are replaced by the observed mean response to the other questions within the Psychological Domain (questions 4, 5, 6, 12, and 13) within each patient and visit. These analyses will mirror those described in this section, with this added convention for these patients.

8.2.5. Analysis of International Consultation on Incontinence Modular Questionnaire-Short Form (ICIQ-SF) Score

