The change from baseline to in the ICIQ-SF Score will be summarized using the primary analysis framework for the FAS. Given that ICIQ-SF is only collected at baseline and at Visit 6, it is not necessary to include the fixed effect of week and the interaction between treatment group and week as fixed effects.

The 3 ordinal responses to the ICIQ-SF will be summarized using descriptive statistics at each visit by treatment group for the FAS. Subgroup analyses of 1) female patients and male patients and 2) patients with at least 1 symptom at baseline and patients with no symptoms at baseline will be conducted.

As well, the non-ordinal responses to the ICIQ-SF (question 6) will be summarized by the number and percent of patients experiencing symptoms at each visit for the FAS. This summary will be repeated within the following subgroups 1) female patients and male patients and 2) patients with at least 1 symptom at baseline and patients with no symptoms at baseline.

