8.2.6. Analysis of Short Form 36, Version 2 (SF-36v2) Scores

The analyses of SF-36v2 scores will use normalized scores provided by Optum, which are based on the 2009 standard normalization scores.

The change from baseline in the Physical Component Summary (PCS) score from the SF-36 responses will be summarized using the primary analysis framework for the FAS. As well, the Mental Component Summary (MCS) score, and the 8 domain scores (see section 3.2.2) will be analyzed in the same manner. Given that SF-36 is only collected at baseline and at Visit 6, it is not necessary to include the fixed effect of week and the interaction between treatment group and week as fixed effects.

The PCS, MCS, and 8 domain scores will be summarized using descriptive statistics at baseline and at Visit 6 by treatment group for the FAS.

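### The secondary change-score models for cough VAS, LCQ, ICIQ-SF and SF-36 adjust for baseline cough count but not for the score's own baseline, which gives up some precision at no gain

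*SAP*

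**What the plan says.** SAP 8.1.1 defines the primary mixed model. Besides treatment, week, their interaction and patient, it has "region and the common logarithm of the frequency of coughs per hour at baseline as covariates". SAP 8.2 makes this model the framework for many secondary endpoints, with the rule "In such cases, the only difference will be response being modelled, unless otherwise noted".

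The sections that invoke the framework note these exceptions:

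- Weekly VAS (SAP 8.2.3): the change "to that at baseline will be analyzed using the primary analysis framework for the FAS". No exception.
- Daily VAS (SAP 8.2.3): the same model, "only using Day 7 in place of Visit 6".
- LCQ (SAP 8.2.4): change in each domain and "the LCQ total score will be analyzed using the primary analysis framework for the FAS". No covariate exception.
- ICIQ-SF (SAP 8.2.5): "Given that ICIQ-SF is only collected at baseline and at Visit 6, it is not necessary to include the fixed effect of week", and the treatment-by-week term is dropped with it.
- SF-36 (SAP 8.2.6): "Given that SF-36 is only collected at baseline and at Visit 6, it is not necessary to include the fixed effect of week", with the same consequence, for PCS, MCS and the 8 domains.

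None of them adds the baseline of the score being analysed or substitutes it for the cough count. Protocol 9.10.3.2 describes the method only as similar to the primary one and names no covariates. SAP 13 declares no departure from the protocol. The sensitivity analyses in SAP 8.1.2 concern the primary endpoint only.

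**The concern.** The primary endpoint is adjusted for its own baseline. These scores are adjusted for the baseline of a different variable. Taken literally, the SAP has the programmer regress change in the SF-36 Mental Component Summary on baseline cough frequency while leaving out the baseline Mental Component Summary.

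A change score is usually negatively related to its own baseline. Leaving that baseline out keeps explainable variation in the residual and lets part of a chance difference between arms at baseline carry into the treatment contrast. SAP 8.2 requires confidence intervals and p-values from these models. In a dose-selection study with one shared placebo arm, a chance imbalance in placebo moves all three dose contrasts together. For LCQ total and Psychological domain the main analysis also excludes the Ukrainian patients (SAP 8.2.4), so any loss falls on a smaller sample.

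**Working it through.** **The plan's own figure.** SAP 4.1 gives a difference of −0.163, SD 0.371, two-sided 5% and 80% power. The normal approximation gives 82 per arm and the t-based calculation gives 83 (power 0.803). Then 83/0.9 = 92.2, rounded up to 93, and 4 × 93 = 372. The stated sample size reproduces. It concerns the primary endpoint; the documents give no precision or power for the patient-reported scores.

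**Assumptions.** None of the following is in the documents: r, the correlation of the score between baseline and Visit 6; c, the correlation of baseline cough count with the baseline score; k, baseline SD divided by follow-up SD. The cough count is taken to act on follow-up only through the baseline score, and only Visit 6 is considered.

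**Equal variances (k = 1, follow-up SD = 1).**

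- Planned residual variance of the change: 2(1 − r) − c²(1 − r)²
- With own baseline added: 1 − r²
- At c = 0 the ratio, adjusted over planned, is (1 + r)/2
- SE increase: 1/√ratio − 1. Worth of 83 patients: 83 × ratio

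| r | c | planned | adjusted | ratio | planned SE larger by | 83 per arm worth |
|---|---|---|---|---|---|---|
| 0.3 | 0 | 1.400 | 0.910 | 0.650 | 24.0% | 54 |
| 0.3 | 0.5 | 1.277 | 0.910 | 0.712 | 18.5% | 59 |
| 0.5 | 0 | 1.000 | 0.750 | 0.750 | 15.5% | 62 |
| 0.5 | 0.5 | 0.938 | 0.750 | 0.800 | 11.8% | 66 |
| 0.7 | 0 | 0.600 | 0.510 | 0.850 | 8.5% | 71 |
| 0.7 | 0.5 | 0.578 | 0.510 | 0.883 | 6.4% | 73 |
| 0.8 | 0 | 0.400 | 0.360 | 0.900 | 5.4% | 75 |
| 0.8 | 0.5 | 0.390 | 0.360 | 0.923 | 4.1% | 77 |

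An endpoint with 80% power under own-baseline adjustment has Φ(2.80 × √ratio − 1.96) under the planned model: about 62% at the top row and 77% at the bottom.

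**Unequal variances (c = 0).** Planned variance is 1 + k² − 2kr and adjusted variance is 1 − r². The difference is (k − r)², which is zero at k = r. With k = 0.7 and r = 0.5, planned is 1 + 0.49 − 0.70 = 0.79 and adjusted is 0.75. The ratio is 0.949 and the SE is 2.6% larger. A k below 1 is plausible for VAS, because inclusion criterion 5 (Protocol 4.2) requires at least 40 mm at Visits 1 and 2, while follow-up is unrestricted.

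**Imbalance.** The SE of a baseline difference between two arms of 83 is √(2/83) = 0.155 SD, ignoring stratification. Its 95% limit is 1.96 × 0.155 = 0.30 SD. Under equal variances and c = 0, (1 − r) of it stays in the change difference. At r = 0.5 a one-SE imbalance shifts the estimate by about 0.08 SD and one at the 95% limit by about 0.15 SD.

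**Simulation (83 per arm, 4,000 runs, no true effect).** For (r, c) = (0.5, 0), (0.5, 0.3), (0.6, 0.3) and (0.7, 0.3):

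- Variance ratios were 0.76, 0.76, 0.83 and 0.86, against 0.75, 0.77, 0.82 and 0.86 by formula.
- The slope of the planned estimate on the imbalance was −0.50, −0.46, −0.35 and −0.29. With own baseline added it was within 0.014 of zero.
- The mean estimate was within 0.002 of zero under both models.

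**The case against.** The strongest reply is that the planned models are valid. Over repeated randomizations the estimates are unbiased and the intervals keep their coverage. The primary endpoint, on which the dose objective rests, has its own baseline in the model. No power is claimed for the secondary scores, and Protocol 7.7 calls ICIQ-SF exploratory. All of this stands, and it makes the point one of efficiency and clarity.

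The cough count is also a reasonable covariate, since it is close to a stratification factor (SAP 4.2). That supports keeping it, but does not make it a substitute: in the table it recovers only part of the loss. Baseline VAS and LCQ (SAP 6.2), ICIQ-SF (8.2.5) and SF-36 (8.2.6) are summarised by arm, so an imbalance would be visible, though still unadjusted. The protocol's looser wording would allow own baselines, and the authors may have intended them. The SAP sentence is more specific, and if that was the intention it needs the same correction.

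Stronger readings that a reader might infer, and that the documents do not support:

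- *Chance imbalance passes in full into the treatment difference.* The response is a change score, so only about (1 − r) of it remains under equal variances.
- *The shift is a second harm on top of the lost precision.* It is the mechanism of the larger standard error, and the reported interval already allows for it.
- *A definite share of the patients is thrown away.* That needs r and k, and neither is given.
- *ICIQ-SF must be the worst case because a patient at 0 can only worsen.* Nothing in the documents allows this to be computed. Patients who stay at 0 would raise r and shrink the loss, and a linear baseline term does not cure a floor. SAP 8.2.5 also plans subgroups by baseline symptoms.

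**Conclusion.** The textual point holds: as written, no VAS, LCQ, ICIQ-SF or SF-36 change model contains the score's own baseline. The consequence is lost precision and a partial carry-over of chance imbalance, without systematic bias.

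The size is an assumption. With equal variances, r from 0.3 to 0.8 and c from 0 to 0.5, planned standard errors are about 4% to 24% larger. With restricted baseline spread the loss can be a few percent (2.6% at k = 0.7, r = 0.5), and it vanishes at k = r. The calculation uses one visit and linear relations, so it is approximate for the repeated-measures models and for a bounded score such as ICIQ-SF. This is a free improvement that should be made before unblinding. It does not put the primary result or the validity of the secondary tests in doubt.

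**What to change.** In SAP 8.2, amend the carry-over rule to say that, for VAS, LCQ, ICIQ-SF and SF-36, the model also includes the baseline value of the score being analysed (the matching domain or component where one is analysed), and keeps region and log10 baseline cough frequency.

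For the awake and asleep ratios, state that the baseline covariate is the log10 baseline awake or asleep rate respectively. SAP 8.1.1 does not carry over the 24-hour qualifier that Protocol 9.10.3.1 attaches to this covariate, so the SAP can be read either way.

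The cost is one or two sentences and one covariate per model. No data are added and no patient is lost, because a change score cannot be computed without its baseline. The edit should be dated before unblinding, since covariates chosen afterwards could look data-driven.
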